#### Clinical Laboratory Evaluation

Observed values and change from baseline will be summarized for each visit, where change from baseline is the result of interest minus baseline value (Visit 2/Day 0 from protocol 093-045 or 093-046).

Each laboratory result will be cross referenced with laboratory-provided normal reference ranges to determine whether the test result is below, within, or above the normal range. Similarly, sponsor defined-potentially clinically significant (PCS) laboratory results will be identified using the criteria in Table 2.

Additionally, the number and percent of the subjects with normal baseline (Visit 2/Day 0 from protocol 093-045 or 093-046) sodium levels reaching the following post-baseline blood sodium levels as below categories will be identified by time point:

- $\leq 135$  mEq/L and  $> 130$  mEq/L
- $\leq 130$  mEq/L and  $> 125$  mEq/L
- $\leq 125$  mEq/L
- $> 10$  mEq/L reduction (i.e.  $< -10$  mEq/L) from baseline

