### 3.3. Determination of Sample Size

Subjects will continue on to this study from Protocols 093-045 or 093-046 as of their own choosing. Therefore, the sample size is outside of statistical considerations.

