### 7.7.2 Clinical Laboratory Evaluation

Descriptive statistics for test results and change from baseline (Visit 2/Day 0 from protocol 093-045 or 093-046) will be displayed at each scheduled visit (i.e. Visit 3-Visit 7) for each continuous laboratory parameter.

The normal reference ranges for laboratory tests will be used to determine whether the laboratory test value is below, within, or above the normal range. Shifts from baseline to each visit will be produced to show the percentage of subjects with laboratory test values below, within, and above the normal range. The percentage will be based on the number of subjects with a baseline result and at least one post-baseline result for each parameter.

Clinical significance of post-baseline abnormally low and high values will be summarized for each lab parameters.

A listing of urine drug screen and serum pregnancy test results will also be provided.

For laboratory parameters with categorical outcomes, the number and percentage of subjects with each outcome will be presented.

The number and percentage of subjects with PCS criteria will be summarized by overall, and by the subgroups including age group, race, gender, number of baseline AED and baseline AEDs.

The listing of the Special Interest of Elevation defined as elevation of any post-dose AST or ALT > 3x ULN will be provided.

Listing of clinical laboratory measurements (hematology, serum chemistry, urinalysis, blood coagulation, bone turnover marker measurements) will be provided.

In addition, listing of clinically significant out of range laboratory measurements, laboratory comments, and listing of subjects meeting any of the PCS lab criteria will be provided.

In addition to continuous summaries of blood sodium levels, the number and percentage of subjects with normal baseline sodium level and a post-baseline level  $\leq 135$  mEq /L but  $> 130$  mEq /L,  $\leq 130$  mEq /L but  $> 125$  mEq /L,  $\leq 125$  mEq /L, and  $> 10$  mEq/L reduction (i.e.  $< -10$  mEq/L) from baseline will be summarized by time point and overall post-baseline.

Above blood sodium levels will be also summarized by baseline AED and for actual monotherapy used subgroup.

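### The graded sodium table covers only subjects with normal baseline sodium, so a low-baseline fall to 127-130 mEq/L, or a fall of more than 10 mEq/L from an above-normal baseline that ends above 126, is in no threshold count

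*SAP*

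**What the plan says.** SAP section 5.3.2 (Clinical Laboratory Evaluation) introduces four sodium rows with one stem, "the number and percent of the subjects with normal baseline (Visit 2/Day 0 from protocol 093-045 or 093-046) sodium levels reaching the following" levels. The first three rows are bands: above 130 to 135, above 125 to 130, and 125 mEq/L or below. The fourth is a reduction of more than 10 mEq/L from baseline. Section 7.7.2 repeats the restriction, planning "the number and percentage of subjects with normal baseline sodium level and a post-baseline level" in each category, by time point and overall. It adds: "Above blood sodium levels will be also summarized by baseline AED and for actual monotherapy used subgroup".

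Three other planned outputs for sodium carry no normal-baseline condition:

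- The PCS low limit in Table 2 is 126 mEq/L or below. Section 7.7.2 says: "The number and percentage of subjects with PCS criteria will be summarized by overall, and by the subgroups including age group", with race, gender, number of baseline AEDs and baseline AEDs completing the list. Subjects meeting any PCS laboratory criterion are also listed.
- The shift table uses only three classes relative to the laboratory limits: "Shifts from baseline to each visit will be produced to show the percentage of subjects with laboratory test values below, within, and above". Its percentages are based on subjects with a baseline and at least one post-baseline result.
- Continuous sodium values and changes from baseline are summarized by visit.

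The normal range itself is not printed: "Each laboratory result will be cross referenced with laboratory-provided normal reference ranges".

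**The concern.** Safety is the primary objective (SAP section 2.1), and sodium is the only laboratory test given its own graded categories. A restriction to normal baseline suits a question about new abnormality. Here, though, it governs every row, including thresholds the subject had not crossed at baseline and the change row, which measures a fall rather than a level.

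The same SAP is less strict for QTc. In the 12-Lead ECG part of section 5.3.2 and in section 7.7.3, a subject is left out of a threshold row only if that threshold was already exceeded at baseline, and the change rows have no baseline condition. No reason is given for treating sodium differently.

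At stake is whether the threshold counts show every subject whose sodium moved into a lower band or fell by more than 10 mEq/L.

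**Working it through.** The SAP gives no figure to reproduce, so the check applies the counting rules to example values.

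**Inputs.** The row limits and the normal-baseline condition come from sections 5.3.2 and 7.7.2, and PCS low (126 or below) from Table 2. The normal range is an assumption: lower limit 135 and upper limit 145 mEq/L in the examples, with the lower limit then varied from 132 to 140. Values are whole numbers.

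**Step 1: examples.**

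| Baseline to post-baseline | Change | Graded sodium rows | PCS low | Shift table |
|---|---|---|---|---|
| 140 to 124 | -16 | 125 or below; fall above 10 | yes | within to below |
| 134 to 123 | -11 | none | yes | below to below |
| 134 to 127 | -7 | none | no | below to below |
| 133 to 128 | -5 | none | no | below to below |
| 148 to 136 | -12 | none | no | above to within |

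A subject going from 135 to 127 would be counted in the row for above 125 to 130. One starting a single unit lower, at 134, is not.

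**Step 2: which low-baseline cases does PCS low recover?** Any value of 125 or below also satisfies 126 or below, so the lowest row is always recovered. For the change row, let L be the lower limit of normal. A low baseline is at most L - 1, and a fall of more than 10 is at least 11, so the end value is at most L - 1 - 11 = L - 12. This is 126 or below whenever L is 138 or below. With L = 135 the end value is at most 123.

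Listing every low-baseline pair (baseline from 115 up to L - 1, end value from 100 up) that reaches 125 or below or falls by more than 10 gives the same result. With L = 135 there are 465 such pairs: none is in any graded row, and all 465 meet PCS low. PCS low misses none for L from 132 to 138, 1 pair at L = 139 (138 to 127) and 3 at L = 140. These are counts of possible value pairs, not of subjects.

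**Step 3: what is left for low baselines?** The second row covers 126 to 130, and PCS low takes 126. That leaves 127 to 130 with no threshold count.

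**Step 4: above-normal baselines.** A fall from 148 to 136 is 12 mEq/L. It is outside the graded table because 148 is not normal, and outside PCS low because 136 is above 126. For baselines 146 to 155 there are 405 pairs that reach 125 or below or fall by more than 10. Of these, 135 end above 126 and so escape both counts. In the example the shift table shows a return to normal.

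**The case against.** The strongest reply is that the restriction is a deliberate incident-event rule and that the serious cases are covered elsewhere. Much of this stands. A reader might infer from the table that a low-baseline subject who reaches 125 or below, or falls by more than 10, goes unreported. The documents do not support that. PCS low counts and lists every value of 125 or below and breaks it down by baseline AED, and for lower limits up to 138 it also captures every low-baseline fall of more than 10. Continuous summaries, the summary of clinical significance of abnormal values and adverse event tables add further coverage.

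A reader might also infer that the comparison across baseline AEDs is distorted because groups differ in how many began low. The wording most naturally makes normal-baseline subjects the denominator. The percentage is then an incidence among those subjects and does not depend on how many others began low. The distortion would need an all-subject denominator, which the SAP does not state.

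A third inference is that the actual monotherapy subgroup has no PCS count to fall back on. Its own list in section 6.5 names only the minimum post-dose sodium change, but the opening sentence of 6.5 plans PCS laboratory parameters for the subgroups that follow. The text is unclear rather than silent.

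Finally, an unchanged normal value of 135 would enter the first row only if the laboratory's lower limit is 135 or less, and the documents do not show that limit.

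The reply does not reach the cases in steps 3 and 4. The QTc parallel supports an incident-event rule for thresholds already crossed, but not removal from every row.

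**Conclusion.** The point holds as a modest gap in a descriptive safety table. Sections 5.3.2 and 7.7.2 leave two kinds of subject in no threshold count: those with low baseline sodium who reach 127-130 mEq/L, and those with above-normal baseline who fall by more than 10 and end above 126.

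The low-baseline result assumes whole-number values and a lower limit of normal no higher than 138; at 139 or 140 a few falls of more than 10 escape as well. The 148 to 136 example assumes an upper limit of 145.

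The number of subjects cannot be estimated. The documents give neither the proportion starting outside the normal range nor their risk of a further fall, so any percentage would rest wholly on assumed inputs. The documents also do not support saying that severe hyponatraemia is missed or that comparisons between baseline AED groups are biased.

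**What to change.** In SAP sections 5.3.2 and 7.7.2:

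1. Keep the four rows for normal-baseline subjects, and state that their percentages use normal-baseline subjects as the denominator.
2. Add one table for all subjects with a baseline and at least one post-baseline sodium value, crossing baseline category with worst post-baseline category. Set the top boundary at the laboratory's lower limit of normal, then use 130 and 125 as now. A fixed boundary at 135 could class a normal 135 as low. Crossing with baseline keeps pre-existing low sodium from being read as new.
3. Count the fall of more than 10 mEq/L in all such subjects, whatever their baseline, overall, by baseline AED and for the actual monotherapy subgroup.

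The cost is one more table from data already collected. The downside is that reported low-sodium counts may rise.

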**Table 2: PCS Criteria for Laboratory Parameters**

Parameter Name	PCS Low	PCS High
Hematology		
WBC	$\leq 2.8 \times 10^9/L$	$\geq 16 \times 10^9/L$
Neutrophils	$< 1.5 \times 10^9/L$	$> 13.5 \times 10^9/L$
Lymphocytes	N/A	$> 12 \times 10^9/L$
Monocytes	N/A	$> 2.5 \times 10^9/L$
Eosinophils	N/A	$> 1.6 \text{ k/mm}^3$
Basophils	N/A	$> 1.6 \text{ k/mm}^3$
Hemoglobin for Females	$\leq 9.5 \text{ g/dL}$	$\geq 17.5 \text{ g/dL}$
Hemoglobin for Males	$\leq 11.5 \text{ g/dL}$	$\geq 19.0 \text{ g/dL}$
Hematocrit for Females	$\leq 32\%$	$\geq 54\%$
Hematocrit for Males	$\leq 37\%$	$\geq 60\%$
RBC	$\leq 3.5 \times 10^{12}/L$	$\geq 6.4 \times 10^{12}/L$
Platelet Count	$\leq 75 \times 10^9/L$	$\geq 700 \times 10^9/L$
Chemistry		
Sodium	$\leq 126 \text{ mEq/L}$	$\geq 156 \text{ mEq/L}$
Potassium	$\leq 3 \text{ mEq/L}$	$\geq 6 \text{ mEq/L}$
Chloride	$\leq 90 \text{ mEq/L}$	$\geq 118 \text{ mEq/L}$
Calcium	$< 8.2 \text{ mg/dL}$	$\geq 12 \text{ mg/dL}$
AST	N/A	$\geq 3 \times \text{ULN}$
ALT	N/A	$\geq 3 \times \text{ULN}$
Alkaline phosphatase	N/A	$\geq 3 \times \text{ULN}$
Creatinine	N/A	$\geq 2 \text{ mg/dL}$
BUN	N/A	$\geq 30 \text{ mg/dL}$
Total bilirubin	N/A	$\geq 2 \text{ mg/dL}$
Total protein	$\leq 4.5 \text{ g/dL}$	$\geq 10 \text{ g/dL}$
Albumin	$\leq 2.5 \text{ g/dL}$	N/A
Glucose	$\leq 40 \text{ mg/dL}$	$\geq 175 \text{ mg/dL}$
Creatinine Phosphokinase	N/A	$> 2.5 \times \text{ULN}$

Phosphate	< 2.0 mg/dL	> 5.3 mg/dL
HDL-Cholesterol	< 30 mg/dL	N/A
LDL-Cholesterol	N/A	> 160 mg/dL
Total Cholesterol	> 300 mg/dL	N/A
Triglycerides	N/A	> 2.5 x ULN
Blood Coagulation		
aPTT	N/A	> 1.5 ULN
INR	N/A	> 1.5 ULN
Thyroid Function		
Free T3	< 0.20 ng/dL	> 0.415 ng/dL
Free T4	< 0.75 ng/dL	> 1.75 ng/dL

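### SAP Table 2 places the total cholesterol limit (> 300 mg/dL) under PCS Low with no PCS High limit, so any PCS output that shows direction would mislabel it

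*SAP*

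**What the plan says.** SAP Section 5.3.2 (Clinical Laboratory Evaluation) makes Table 2 the operative rule: "sponsor defined-potentially clinically significant (PCS) laboratory results will be identified using the criteria in Table 2". The table's header is "Parameter Name PCS Low PCS High". The four lipid rows, in order, are:

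- first, with its limit under Low: "HDL-Cholesterol < 30 mg/dL N/A"
- second, with its limit under High: "LDL-Cholesterol N/A > 160 mg/dL"
- third, the row at issue here: "Total Cholesterol > 300 mg/dL N/A"
- fourth, with its limit under High: "Triglycerides N/A > 2.5 x ULN"

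Section 7.7.2 reports the result: "The number and percentage of subjects with PCS criteria will be summarized by overall, and by the subgroups", the subgroups being age group, race, gender, number of baseline AEDs and baseline AEDs. It also calls for a listing of subjects who meet any PCS laboratory criterion. It does not say whether the summary or the listing is split into low and high.

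A second classification runs alongside and does not use Table 2. On the comparison with the laboratory's own limits, Section 5.3.2 states: "Each laboratory result will be cross referenced with laboratory-provided normal reference ranges to determine whether the test result is below, within, or above the normal". Section 7.7.2 builds shift tables on it and adds descriptive statistics by visit.

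**The concern.** The limit's operator and its column contradict each other. A value has to be high to exceed 300 mg/dL, yet the table files it as low and leaves the high side empty. The SAP has no sentence explaining how a laboratory value is judged PCS low or PCS high, so the table alone gives the programmer the direction.

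Lipids are a scheduled safety measurement (Section 5.1), are named among the safety variables (Section 7.7), and belong to a study whose primary objective is safety and tolerability (Section 2.1). PCS laboratory parameters are also a subgroup outcome (Section 6.5). At stake is whether a reader of the PCS output sees marked hypercholesterolaemia labelled as such, or labelled as an abnormally low value.

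**Working it through.** No sample size, power or error rate is involved and the plan gives no figure to reproduce. The check is a count of operators by column, then an application of the row to example values.

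**Step 1. Operators in Table 2, all rows.** The table has 12 haematology, 19 chemistry and lipid, 2 coagulation and 2 thyroid rows: 12 + 19 + 2 + 2 = 35 parameters.

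| Column | Rows with a limit | Using < or ≤ | Using > or ≥ |
|---|---|---|---|
| PCS Low | 20 | 19 | 1 (total cholesterol) |
| PCS High | 32 | 0 | 32 |

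Three rows have no High limit (35 − 32 = 3): albumin, HDL-cholesterol and total cholesterol. Albumin (≤ 2.5 g/dL) and HDL-cholesterol (< 30 mg/dL) have genuine low limits. Total cholesterol is the only row whose operator contradicts its column.

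**Step 2. Could the extracted text have shifted the cells?** The rows on either side are aligned as expected: HDL-cholesterol has its limit under Low, and LDL-cholesterol and triglycerides have theirs under High. The total cholesterol row has all three cells filled, with an explicit N/A in the last. A reading error would have had to swap two cells in this one row. That is unlikely, though it cannot be excluded from the extracted text, because the header is not repeated above this part of the table.

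**Step 3. Apply the row to example values** (chosen for illustration, not trial data), keeping the printed operator.

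| Total cholesterol (mg/dL) | As written | With the two cells swapped |
|---|---|---|
| 150 | not flagged | not flagged |
| 250 | not flagged | not flagged |
| 301 | PCS Low | PCS High |
| 350 | PCS Low | PCS High |

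The condition is value > 300 in both versions, so the set of flagged subjects is identical. Only the direction label changes.

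**Step 4. The table after the swap.** Low limits: 20 − 1 = 19, all < or ≤. High limits: 32 + 1 = 33, all > or ≥. No row then contradicts its column.

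**Step 5. Where the label could reach.** It reaches any PCS summary or listing that separates low from high. It does not reach a count of subjects meeting any PCS criterion, the shift tables or the by-visit statistics.

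**The case against.** The best case for leaving this alone is that it may change no reported number. Section 7.7.2 speaks of subjects meeting PCS criteria and does not call for a low/high split. If the output is an any-criterion count with the printed operator, it is correct already. The lipid panel is also not part of routine visits after Month 12 (Section 5.1), and the safety analysis is descriptive (Section 7.7), so no formal conclusion depends on this row. All of that stands and limits the size of the point. It does not make the row right: Table 2 itself separates Low from High, so a directional output is a natural way to program it.

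Three stronger readings are tempting, and the documents do not support them.

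- *A reader might infer that raised cholesterol would never be reported as high.* That is true only within the PCS classification. The normal-range classification and its shift tables would show it as above normal, and Section 7.7.2 separately summarises the clinical significance of abnormally low and high values. These outputs do not replace the PCS flag, because the shift tables use the laboratory's normal limits and not the 300 mg/dL threshold.
- *A reader might infer that the PCS High table would show a false 0%.* The SAP does not specify such a table, and N/A means that no criterion exists, as it does for albumin and HDL-cholesterol. It is not a computed zero.
- *A reader might infer that nearly every subject would be flagged PCS Low, if the program takes low to mean below the limit.* Section 5.3.2 states such a rule only for vital signs, where it is paired with a change-from-baseline condition that Table 2 does not have. For laboratory results the SAP says only that the Table 2 criteria are used, and each carries its own operator. This outcome would require the programmer to discard the printed > sign.

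**Conclusion.** The point holds in a limited form. Table 2 contradicts itself in the total cholesterol row and no other part of the SAP corrects it. Because Table 2 is the rule by which PCS results are identified, it is wrong as written and should be corrected.

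The impact is minor: a direction label on one parameter in descriptive safety output. This rests on two assumptions: that the program applies the printed operator, and that the extracted row matches the source PDF. How many subjects would carry the wrong label cannot be estimated, since the documents give no cholesterol data.

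**What to change.** Check the row against the source PDF. Then, in Table 2, put > 300 mg/dL under PCS High and N/A under PCS Low for total cholesterol, leaving the threshold value as it is. Make the same change in the programmed criteria file, and check that the PCS summary and listing carry the flag as high wherever they show direction.

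The cost is two cells in one table row and one entry in the criteria file. No data collection, analysis population or other analysis changes.

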### 12-Lead ECG

Observed values and change from baseline will be summarized for each visit, where change from baseline is the result of interest minus the baseline result (Visit 2 from protocol 093-045 or 093-046).

The number and percentage of subjects with QTc-F values in the following categories will be identified:

- QTc-F >500 ms at any postdose time point not present at baseline
- QTc-F >480 ms at any postdose time point not present at baseline
- QTc-F >450 ms at any postdose time point not present at baseline
- Change from baseline in QTc-F  $\geq$ 60 ms for at least 1 postdose measurement
- Change from baseline in QTc-F  $\geq$ 30 ms for at least 1 postdose measurement, but <60 ms for all postdose measurements.

This categorical analysis will be also performed for QTc-B.

The incidence of specific ECG abnormalities will also be identified for the following categories:

- Overall abnormalities
- Rhythm abnormalities
- Conduction abnormalities
- Morphology abnormalities
- Myocardial infarction
- Presence of ST Segment abnormalities
- Presence of T wave abnormalities
- Presence of U wave abnormalities

### Vital Signs

Observed values and change from baseline will be summarized for each visit, where change from baseline is the result of interest minus the baseline result (Visit 2 from protocol 093-045 or 093-046).

In addition, subjects meeting the sponsor defined vital sign PCS criteria (Table 3) will be identified.

A vital sign value is considered PCS low if it is below the specified low limit and it decreases from baseline more than the specified decrease from baseline limit. A vital sign value is considered PCS high if it is higher than the specified high limit and it increases from baseline more than the specified increase from baseline limit.

**Table 3: PCS Criteria for Vital Signs**

Parameter Name	Low	Decrease from Baseline	High	Increase from Baseline
Supine Systolic BP	< 90 mm Hg	≥ 20 mm Hg	> 180 mm Hg	≥ 20 mm Hg
Supine Diastolic BP	< 50 mm Hg	≥ 15 mm Hg	> 105 mm Hg	≥ 15 mm Hg
Supine Heart Rate	< 50 bpm	≥ 15 bpm	> 120 bpm	≥ 25 bpm
Weight	N/A	≥ 7%	N/A	≥ 7%

### Body Weights

Observed weight values and change from baseline will be summarized for each visit, where change from baseline is the weight at the visit of interest minus the baseline weight (Visit 2 from protocol 093-045 or 093-046). Subjects with a weight change of ≥7% will be identified at each visit by dividing the change from baseline weight, by the baseline weight, and multiplying by 100.

### Orthostatic Effects

The number and percentage of subjects who experienced orthostatic hypotension and orthostatic tachycardia will be summarized. Orthostatic effects can be determined for a vital sign, by examining the difference between positions.

(Standing result during the interval of interest)- (Supine result during the interval of interest)

Orthostatic hypotension is having a difference of ≤ -20 mmHg in systolic or ≤ -10 mmHg in diastolic blood pressure. Orthostatic tachycardia will be defined as a difference in heart rate ≥ 20 beats per minute and the standing heart rate >100 beats per minute after the subject was standing for at least 2-4 minutes.

